4.3. Intrapatient Dose Modification

Every effort should be made to administer study treatment on the planned dose and schedule.

4.3.1. Dosing Delays and Interruptions

Study treatment dosing delays will be permitted in any treatment cycle if unforeseen circumstances prevent the patient from returning to the clinic on the scheduled day(s). A maximum delay of 2 days in Cycle 1 will be permitted. If administration of study treatment is delayed by > 2 days in Cycle 1, that dose is considered missed and the patient should receive the next dose at the next visit.

If a patient misses ≥ 2 SYNB1891 doses in Cycle 1, then the patient will be discontinued permanently from treatment and may be replaced (see Section 8.2.1). In Cycle 2 and beyond, if a patient misses the dose of SYNB1891, then the patient may be discontinued permanently from treatment, unless the Investigator's assessment of the benefit/risk suggests otherwise (after consultation with Sponsor). If treatment is permanently discontinued, patients will continue to be followed for safety as indicated for end of treatment and follow-up.

SYNB1891 treatment interruption can occur due to treatment-related toxicity, including Grade 3 or higher infections or local inflammation requiring antibiotics, and the start of a new cycle may not occur until the following criteria have been met:

- Nonhematologic toxicities have returned to either baseline or Grade ≤ 1 , or at the Investigator's discretion, Grade ≤ 2 if not considered a safety risk. This condition must be met within 14 days of the initial treatment interruption.
- Hematologic toxicities: ANC $\geq 1000/\text{mm}^3$ or have returned to baseline levels; platelet count $\geq 50,000/\text{mm}^3$ or has returned to baseline levels. This condition must be met within 14 days of the initial treatment interruption.
- If a patient requires treatment with a systemic antibiotic on study, SYNB1891 should be held for the duration of the antibiotic regimen and for 5 half-lives after the last dose of antibiotics. Once the patient is apyretic after completion of the antibiotic washout period, SYNB1891 may resume.

If the patient cannot meet the above conditions within the specified time frame, then study treatment should be permanently discontinued, unless the Investigator's assessment of the benefit/risk suggests otherwise (after consultation with Sponsor). The patient may be replaced (see Section 8.2.1).

Atezolizumab treatment may be temporarily suspended in patients experiencing toxicity considered to be related to study treatment. If corticosteroids are initiated for treatment of immune-mediated toxicity, they must be tapered over ≥ 1 month to the equivalent of ≤ 10 mg/day oral prednisone before atezolizumab can be resumed. If atezolizumab is withheld for > 12 weeks after event onset, the patient will be discontinued from atezolizumab. However, atezolizumab may be withheld for > 12 weeks to allow for patients to taper off corticosteroids prior to resuming treatment. Atezolizumab can be resumed after being withheld for > 12 weeks if the Medical Monitor(s) agrees that the patient is likely to derive clinical benefit. Atezolizumab treatment may be suspended for reasons other than toxicity (e.g., surgical procedures) with Medical Monitor approval. The Investigator and the Medical Monitor(s) will determine the acceptable length of treatment interruption.

4.3.2. Dose Reductions

4.3.2.1. Dose Reductions for SYNB1891

No dose reductions of SYNB1891 will be permitted in Cycle 1; any patient who requires such a modification will be permanently discontinued and may be replaced (see Section 8.2.1). After Cycle 1, SYNB1891 dose reductions are permitted in approximately 3-fold decrements after consultation with the Sponsor. While no specific dose reductions are required for Grade 1 or 2 treatment-related toxicities, the Investigator should always manage patients according to medical judgment and assessment of risk/benefit for that patient. Patients experiencing recurrent or intolerable Grade 2 toxicity may resume dosing at the next lower dose level once the toxicity has resolved or recovery to Grade 1 or baseline has occurred.

If more than 1 dose reduction is required, then the patient(s) are permanently discontinued from treatment but will be followed for end of treatment and follow-up assessments.

Once a dose has been reduced, the patient should continue to receive that dose for all subsequent doses. In this setting, intrapatient dose escalation is not permitted.

4.3.2.2. Dose Reductions for Atezolizumab

No dose reductions of atezolizumab will be permitted in this study.

4.4. Toxicity Management

Participants should receive appropriate supportive care measures as deemed necessary by the treating Investigator.

4.4.1. Adverse Events Associated with SYNB1891

Guidelines for the management of patients who experience AEs considered to be potentially associated with SYNB1891 are provided in [Table 2](#).

Table 2: Toxicity Management for Adverse Events Considered Potentially Associated with SYNB1891

Event	NCI CTCAE Grade	Recommended Medical Management	Premedication and Subsequent Dosing
Cytokine release syndrome (may include associated AEs, e.g., fever, tachypnea, headache, tachycardia, hypotension, rash, hypoxia)	Grade 1 Fever with or without constitutional symptoms	Increase vital sign and oxygen saturation monitoring as medically indicated until the patient is deemed medically stable in the opinion of the Investigator.	Administer as planned
	Grade 2 Hypotension responding to fluids; hypoxia responding to < 40% oxygen	Increase vital sign and oxygen saturation monitoring as medically indicated until the patient is deemed medically stable in the opinion of the Investigator. Additional appropriate therapy may include, but is not limited to: IV fluids NSAIDs Acetaminophen Narcotics Oxygen Evaluate for infectious etiologies and treat neutropenia if present.	Patient may be premedicated 1.5 hours (\pm 30 minutes) prior to study treatment administration with oral acetaminophen (500 to 1000 mg) or equivalent dose of antipyretics.
	Grade 3 Hypotension managed with one pressor; hypoxia requiring \geq 40% oxygen	Appropriate therapy may include, but is not limited to: IV fluids NSAIDs Acetaminophen Narcotics Oxygen Pressors Corticosteroids Anti-IL6 (e.g., tocilizumab) Empiric antibiotics Monitor patients closely; consider an intensive care setting	Discuss with the Sponsor prior to the resumption of study treatment. Upon approval by the Sponsor, resume SYNB1891 at a reduced dose upon AE resolution to baseline or Grade 1. Patient may be premedicated 1.5 hours (\pm 30 minutes) prior to study treatment administration with oral acetaminophen (500 to 1000 mg) or equivalent dose of antipyretics.

Event	NCI CTCAE Grade	Recommended Medical Management	Premedication and Subsequent Dosing
	Grade 4 Life-threatening consequences; urgent intervention indicated	
Appropriate therapy may include, but is not limited to:
 
 IV fluids NSAIDs Acetaminophen Narcotics Oxygen Pressors Corticosteroids Anti-IL6 (e.g., tocilizumab) Empiric antibiotics 
Monitor patients closely; consider an intensive care setting.
	Permanently discontinue study treatment.
Systemic infection	Grade 3 or higher	
Appropriate therapy may include, but is not limited to:
 
 IV fluids NSAIDs Acetaminophen Narcotics Oxygen Pressors Empiric antibiotics Refer to Appendix 4 for EcN-sensitive antibiotics 
Perform local blood and urine cultures and sensitivities.
 
Perform serum qPCR specific for EcN.
	Patients who require systemic antibiotic treatment should postpone dosing with SYNB1891 for the duration of the antibiotic regimen and for 5 half-lives after the last dose of antibiotics and until the patient is apyretic.
Local injection site reactions (may include associated AEs, e.g., abscess, infection, ulceration or necrosis, or severe tissue damage)	Grade 3 or higher	
Consider surgical intervention as needed in addition to and in accordance with local standard of care, which may include, but is not limited to:
 
 NSAIDs Acetaminophen Antibiotics 	Permanently discontinue study treatment.

Abbreviations: AE = adverse event; CTCAE = Common Terminology Criteria for Adverse Events; *EcN* = *E. coli* Nissle; IL = interleukin; IV = intravenous; NCI = National Cancer Institute; NSAID = nonsteroidal anti-inflammatory drug; qPCR = quantitative polymerase chain reaction

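### Table 2 and Section 4.3 of the Protocol disagree on SYNB1891 re-dosing after Grade 3 CRS early in Cycle 1 and after Grade 3 or higher injection-site infection

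*Protocol*

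**What the plan says.** **Grade 3 CRS.** Table 2 (Protocol Section 4.4.1) first tells the site: "Discuss with the Sponsor prior to the resumption of study treatment". It then adds: "Upon approval by the Sponsor, resume SYNB1891 at a reduced dose upon AE resolution to baseline or Grade 1". Neither sentence names a cycle. Section 4.3.2.1 says "No dose reductions of SYNB1891 will be permitted in Cycle 1; any patient who requires such a modification will be permanently discontinued" and, next, "After Cycle 1, SYNB1891 dose reductions are permitted in approximately 3-fold decrements after consultation with the Sponsor". Section 4.2.1 schedules the Cycle 1 injections on Days 1, 8 and 15. Section 4.3.1 lets a Cycle 1 dose be up to 2 days late and counts a later one as missed. Of a patient who misses two or more, it says: "SYNB1891 doses in Cycle 1, then the patient will be discontinued permanently from treatment and may be replaced".

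**Infection and local reaction.** Section 4.3.1 says "SYNB1891 treatment interruption can occur due to treatment-related toxicity, including Grade 3 or higher infections or local inflammation requiring antibiotics" and then lists conditions for starting a new cycle. One of these reads "If a patient requires treatment with a systemic antibiotic on study, SYNB1891 should be held for the duration of the antibiotic regimen", plus a washout of five half-lives. It ends: "Once the patient is apyretic after completion of the antibiotic washout period, SYNB1891 may resume". Table 2 has two relevant rows, both for Grade 3 or higher. The systemic-infection row postpones dosing, in terms close to that bullet. The local injection-site row names abscess and infection among its examples and requires permanent discontinuation.

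**Re-challenge.** Section 8.2 allows treatment to resume after a patient has met permanent-discontinuation criteria for intolerable toxicity. The patient must be deriving benefit and have fully recovered from the immune-related event, and both the Investigator and the Sponsor must document approval.

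**The concern.** SYNB1891 is a live bacterium in its first human study. CRS and Grade 3 or higher injection-site reactions are two of its three adverse events of special interest (Section 9.3). For each, one part of the Protocol holds out further injection while another bars it or orders treatment stopped, and neither part refers to the other. A site that reads only one part could plan a dose that the other does not allow, or commit an avoidable protocol deviation. The Cycle 1 Day 1 case is not remote from what the Protocol expects: Section 4.2.2 requires at least 6 hours of observation after each injection and a telephone call on Cycle 1 Day 3 to look for signs of CRS.

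**Working it through.** The plan states no figure to reproduce. The check compares the texts and counts Cycle 1 doses.

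**Limb 1: Grade 3 CRS in Cycle 1.** Inputs:
- three planned injections, Days 1, 8 and 15 (Section 4.2.1);
- any resumed dose is reduced (Table 2);
- no reduced dose in Cycle 1 (Section 4.3.2.1);
- permanent discontinuation at two or more missed Cycle 1 doses (Section 4.3.1).

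The earliest permitted reduced dose is therefore Cycle 2 Day 1. Doses missed while waiting = 3 − injections already given, assuming no other dose was missed.

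| Event follows | Missed if waiting for Cycle 2 Day 1 | Two-dose limit reached? | Reduced-dose resumption under Section 4.3 |
|---|---|---|---|
| Day 1 | 3 − 1 = 2 of 3 | Yes | Not available |
| Day 8 | 3 − 2 = 1 of 3 | No | Available if Day 15 is omitted, subject to the reading of Section 4.3.2.1 |
| Day 15 | 3 − 3 = 0 of 3 | No | Available |

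After a Day 1 event there are three ways to resume, and each fails:
- a reduced dose on Day 8 or 15 breaches Section 4.3.2.1;
- a full dose on either day departs from Table 2;
- waiting for Cycle 2 Day 1 triggers discontinuation under Section 4.3.1.

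Section 4.3.1 has two benefit/risk exceptions. One covers a missed dose in Cycle 2 or later, and the other covers failure to meet the restart conditions in time. Neither attaches to the Cycle 1 missed-dose rule.

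The Day 8 row depends on what it means to require a reduction. If a patient who could receive Day 15 only at a lower dose counts as requiring one, Section 4.3.2.1 discontinues that patient. If Day 15 is simply omitted, no Cycle 1 reduction takes place and Cycle 2 Day 1 remains open.

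**Limb 2: Grade 3 or higher injection-site infection.**

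| Text | Event covered | Action |
|---|---|---|
| Section 4.3.1, interruption sentence | Grade 3 or higher infection, site not restricted; local inflammation needing antibiotics | Interrupt; restart if conditions are met |
| Section 4.3.1, antibiotic bullet | Any patient needing a systemic antibiotic | Hold, wash out, may resume; no Sponsor step stated |
| Table 2, local row | Grade 3 or higher injection-site reaction, including infection and abscess | Permanently discontinue |

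Table 2 itself lists antibiotics among the treatments for the local event. An injection-site infection treated with a systemic antibiotic therefore falls under all three texts.

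**Does precedence settle it?** No order is stated, and the two obvious orders fail in opposite directions. If Section 4.3 governs, limb 1 resolves safely but limb 2 permits re-injection. If Table 2 governs, limb 2 resolves safely but limb 1 permits a reduced dose in Cycle 1. Only a rule that the stricter text prevails works for both, and the Protocol has no such rule.

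**Effect on dose finding.** A related Grade 3 CRS or Grade 3 local infection in Cycle 1 is already a DLT under item 3 of Section 4.2.4. Section 4.2.3 makes a patient with a DLT evaluable whatever the number of injections. The DLT count and the Table 1 decision are the same whichever re-dosing text is followed.

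**The case against.** The strongest reply is that Table 2 gives general guidelines for all cycles and Section 4.3.2.1 limits them, so that reduced-dose resumption simply means after Cycle 1. The Sponsor must be consulted and must approve before any resumption after Grade 3 CRS. A sentinel patient's data are reviewed on or after Day 7 before further injections, and the Safety Review Committee sees every DLT. These safeguards are real and are the main reason the point is minor. The proposed reading is sensible but is not written down, and carrying the same principle over to limb 2 gives the wrong answer.

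On limb 2, the interruption sentence can be parsed as Grade 3 or higher infections on the one hand, and local inflammation of any grade needing antibiotics on the other. The antibiotic bullet also most naturally serves the systemic-infection row. Both points reduce the overlap without removing it: the word infections is not limited to systemic ones, and nothing ties the bullet to one row.

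A reader might infer three stronger conclusions that the documents do not support:
- *Table 2 itself offers re-injection after serious local reactions.* It does the opposite; the restart wording is in Section 4.3.1.
- *Permanent discontinuation is the only course after a Day 1 event.* Section 8.2 is a possible route, since Section 4.4.2.7 describes CRS as a response to immune therapy. It is narrow: benefit is required, and the first scheduled on-study imaging is at the end of Cycle 2. Because it is tied to immune-related events, it may not reach a bacterial abscess.
- *The share of scheduled injections after which the option is blocked measures risk.* One to two of the six injections in Cycles 1 to 4 is 17% to 33%. Over a full course to Cycle 35 (3 + 34 = 37 injections) the same count is 3% to 5%. Neither says how often the events occur.

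**Conclusion.** The inconsistency is real and minor. After Grade 3 CRS following the Cycle 1 Day 1 injection, the reduced-dose option in Table 2 is unavailable under Section 4.3, apart from the Section 8.2 route. After Day 8 it is available only on one reading of Section 4.3.2.1, and after Day 15 nothing conflicts. For Grade 3 or higher injection-site infection, Section 4.3.1 permits a restart that Table 2 rules out, and its antibiotic bullet states no Sponsor step.

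Permanent discontinuation breaches none of these texts. The documents give no event frequencies, so the number of patients affected cannot be estimated.

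That DLT counts and mTPI decisions are unaffected assumes that the evaluability rule in Protocol Section 4.2.3 governs. SAP Section VIII.B asks for two of three injections before a patient contributes to escalation decisions and does not repeat the DLT alternative. That difference is a separate matter and is not relied on here.

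**What to change.** (a) In Table 2, Grade 3 CRS row, add: *No reduced dose may be given in Cycle 1 (Section 4.3.2.1); reduced-dose resumption applies from Cycle 2 Day 1 and only if fewer than 2 Cycle 1 doses were missed (Section 4.3.1).* This closes the Day 1 case. It leaves the Sponsor to decide whether a patient with a Day 8 event may omit Day 15 and resume; if so, Section 4.3.2.1 should say so.

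(b) In Section 4.3.1, after the interruption sentence, add: *except Grade 3 or higher local injection-site reactions, including infection and abscess, for which study treatment is permanently discontinued (Table 2).* State also that the antibiotic hold-and-resume bullet does not apply to those events.

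Section 8.2 can stay as written. The cost is two wording edits in the next amendment, with no added visits, assessments or patients. The downside is that an occasional patient loses the option of continued dosing.

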4.4.2. Adverse Events Associated with Atezolizumab

4.4.2.1. Pulmonary Events

Dyspnea, cough, fatigue, hypoxia, pneumonitis, and pulmonary infiltrates have been associated with the administration of atezolizumab. Patients will be assessed for pulmonary signs and symptoms throughout the study and will have imaging (e.g., computed tomography [CT] scans) of the chest performed at every tumor assessment.

All pulmonary events should be thoroughly evaluated for other commonly reported etiologies such as pneumonia or other infection, lymphangitic carcinomatosis, pulmonary embolism, heart failure, chronic obstructive pulmonary disease, or pulmonary hypertension. Management guidelines for pulmonary events are provided in [Table 3](#).

Table 3: Management Guidelines for Pulmonary Events, Including Pneumonitis

Event	NCI CTCAE Grade	Recommended Medical Management
Pulmonary event	Grade 1	
 Continue atezolizumab and monitor closely. Re-evaluate on serial imaging. Consider patient referral to pulmonary specialist.
	Grade 2	
 Withhold atezolizumab for up to 12 weeks after event onset.^a Refer patient to pulmonary and infectious disease specialists and consider bronchoscopy or BAL. Initiate treatment with corticosteroids equivalent to 1–2 mg/kg/day oral prednisone. If event resolves to Grade 1 or better, resume atezolizumab.^b If event does not resolve to Grade 1 or better while withholding atezolizumab, permanently discontinue atezolizumab and contact Medical Monitor(s). For recurrent events, treat as a Grade 3 or 4 event.
	Grade 3 or higher	
 Permanently discontinue atezolizumab and contact Medical Monitor(s). Bronchoscopy or BAL is recommended. Initiate treatment with corticosteroids equivalent to 1–2 mg/kg/day oral prednisone. If event does not improve within 48 hours after initiating corticosteroids, consider adding an immunosuppressive agent. If event resolves to Grade 1 or better, taper corticosteroids over ≥ 1 month.

Abbreviations: BAL = bronchoscopic alveolar lavage; CTCAE = Common Terminology Criteria for Adverse Events; NCI = National Cancer Institute

^a Atezolizumab may be withheld for a longer period of time (i.e., > 12 weeks after event onset) to allow for corticosteroids (if initiated) to be reduced to the equivalent of ≤ 10 mg/day oral prednisone. The acceptable length of the extended period of time must be agreed upon by the Investigator and the Medical Monitor(s).

^b If corticosteroids have been initiated, they must be tapered over ≥ 1 month to the equivalent of ≤ 10 mg/day oral prednisone before atezolizumab can be resumed.

4.4.2.2. Hepatic Events

Immune-mediated hepatitis has been associated with the administration of atezolizumab. Eligible patients must have adequate liver function, as manifested by measurements of total bilirubin and hepatic transaminases, and liver function will be monitored throughout study treatment.

Management guidelines for hepatic events are provided in [Table 4](#).

Patients with right upper-quadrant abdominal pain and/or unexplained nausea or vomiting should have liver function tests (LFTs) performed immediately and reviewed before administration of the next dose of study drug.

For patients with elevated LFTs, concurrent medication, viral hepatitis, and toxic or neoplastic etiologies should be considered and addressed, as appropriate.

Table 4: Management Guidelines for Hepatic Events

Event	NCI CTCAE Grade	Recommended Medical Management
Hepatic event	Grade 1	
 Continue atezolizumab. Monitor LFTs until values resolve to within normal limits or to baseline values.
	Grade 2	
All events:
 
 Monitor LFTs more frequently until return to baseline values. 
Events of >5 days duration:
 
 Withhold atezolizumab for up to 12 weeks after event onset.^a Initiate treatment with corticosteroids equivalent to 1–2 mg/kg/day oral prednisone. If event resolves to Grade 1 or better, resume atezolizumab.^b If event does not resolve to Grade 1 or better while withholding atezolizumab, permanently discontinue atezolizumab and contact Medical Monitor(s).
	Grade 3 or higher	
 Permanently discontinue atezolizumab and contact Medical Monitor(s). Consider patient referral to gastrointestinal specialist for evaluation and liver biopsy to establish etiology of hepatic injury. Initiate treatment with corticosteroids equivalent to 1–2 mg/kg/day oral prednisone. If event does not improve within 48 hours after initiating corticosteroids, consider adding an immunosuppressive agent. If event resolves to Grade 1 or better, taper corticosteroids over \geq 1 month.

Abbreviations: CTCAE = Common Terminology Criteria for Adverse Events; LFT = liver function test; NCI = National Cancer Institute

^a Atezolizumab may be withheld for a longer period of time (i.e., > 12 weeks after event onset) to allow for corticosteroids (if initiated) to be reduced to the equivalent of \leq 10 mg/day oral prednisone. The acceptable length of the extended period of time must be agreed upon by the Investigator and the Medical Monitor(s).

^b If corticosteroids have been initiated, they must be tapered over \geq 1 month to the equivalent of \leq 10 mg/day oral prednisone before atezolizumab can be resumed.

4.4.2.3. Gastrointestinal Events

Immune-mediated colitis has been associated with the administration of atezolizumab. Management guidelines for diarrhea or colitis are provided in [Table 5](#).

All events of diarrhea or colitis should be thoroughly evaluated for other more common etiologies. For events of significant duration or magnitude or associated with signs of systemic inflammation or acute-phase reactants (e.g., increased C-reactive protein, platelet count, or bandemia): perform sigmoidoscopy (or colonoscopy, if appropriate) with colonic biopsy, with 3 to 5 specimens for standard paraffin block to check for inflammation and lymphocytic infiltrates to confirm colitis diagnosis.

Table 5: Management Guidelines for Gastrointestinal Events

Event	NCI CTCAE Grade	Recommended Medical Management
Diarrhea or colitis	Grade 1	
 Continue atezolizumab. Initiate symptomatic treatment. Endoscopy is recommended if symptoms persist for > 7 days. Monitor closely.
	Grade 2	
 Withhold atezolizumab for up to 12 weeks after event onset.^a Initiate symptomatic treatment. Patient referral to GI specialist is recommended. For recurrent events or events that persist > 5 days, initiate treatment with corticosteroids equivalent to 1–2 mg/kg/day oral prednisone. If event resolves to Grade 1 or better, resume atezolizumab.^b If event does not resolve to Grade 1 or better while withholding atezolizumab, permanently discontinue atezolizumab and contact Medical Monitor(s).
	Grade 3	
 Withhold atezolizumab for up to 12 weeks after event onset.^a Refer patient to GI specialist for evaluation and confirmatory biopsy. Initiate treatment with corticosteroids equivalent to 1–2 mg/kg/day IV methylprednisolone and convert to 1–2 mg/kg/day oral prednisone or equivalent upon improvement. If event resolves to Grade 1 or better, resume atezolizumab.^b If event does not resolve to Grade 1 or better while withholding atezolizumab, permanently discontinue atezolizumab and contact Medical Monitor(s).
	Grade 4	
 Permanently discontinue atezolizumab and contact Medical Monitor(s). Refer patient to GI specialist for evaluation and confirmation biopsy. Initiate treatment with corticosteroids equivalent to 1–2 mg/kg/day IV methylprednisolone and convert to 1–2 mg/kg/day oral prednisone or equivalent upon improvement. If event does not improve within 48 hours after initiating corticosteroids, consider adding an immunosuppressive agent. If event resolves to Grade 1 or better, taper corticosteroids over ≥ 1 month.

Abbreviations: CTCAE = Common Terminology Criteria for Adverse Events; GI = gastrointestinal; IV = intravenous;

NCI = National Cancer Institute

^a Atezolizumab may be withheld for a longer period of time (i.e., > 12 weeks after event onset) to allow for corticosteroids (if initiated) to be reduced to the equivalent of ≤ 10 mg/day oral prednisone. The acceptable length of the extended period of time must be agreed upon by the Investigator and the Medical Monitor(s).

^b If corticosteroids have been initiated, they must be tapered over ≥ 1 month to the equivalent of ≤ 10 mg/day oral prednisone before atezolizumab can be resumed.

